#### **Inclusion criteria**

1. Inpatient of both sexes are aged from 18 to 65 years;
2. Diagnosis of major depressive disorder(single or recurrent episodes) is made according to DSM-V criteria;
3. Subjects with previous or current depressive episodes did not response to two different antidepressants with recommended doses and adequate duration (maximum treatment dose of at least 6 weeks);
4. The subjects who will score more than or equal to 22 points on the MADRS scale at screening and baseline period;
5. The subjects who will score more than or equal to 3 points on the first clause of MADRS scale at screening and baseline period;
6. Subjects who will sign written informed consent and volunteer to participate in the clinical study.

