#### **Exclusion criteria**

1. Diagnoses of other mental disorders (such as organic mental disorders, schizophrenia, bipolar and related disorders, anxiety disorders, obsessive-compulsive disorders and so on) are made according to DSM-V criteria;
2. Depressive episodes, such as depression caused by hypothyroidism, secondary to a systemic disease or an organic mental disorder caused by a neurological disease;

3. Subjects with a history of attempted suicide, or currently at high suicide risk, or with suicide behavior/attempt, or scoring more than or equal to 3 points on the 10th clause of MADRS scale;
4. Subject whose score of MADRS scale in baseline period will be 25% lower than that in screening period;
5. Subjects with a history of severe or poorly controlled cardiovascular, liver, kidney, blood, endocrine, respiratory diseases, etc;
6. Subjects with a history of epileptic seizures, except for a single febrile convulsion in children;
7. Researchers believe that the results of subjects' physical and laboratory examinations are clinically significant abnormalities in screening or baseline period. The following indicators exceed the following criteria: 1)ALT or AST levels are 1.5 times higher than the upper limit of laboratory normal values. 2)Thyroid Function are 1.1 times higher than the upper or lower limit of normal values. 3) Serum creatinine values are 1.1 times higher than the upper limit of normal values. 4)The levels of blood urea nitrogen are higher than the upper limit of normal values;
8. The result of electrocardiogram (ECG) is abnormal in screening or baseline period, such as male subjects with QTc interval ( $> 450$  ms) and female subjects with QTc interval ( $> 470$  ms) , and the researchers thought it is not suitable for selection;
9. Subjects could not swallow oral medicines or have a history of gastrointestinal surgery or any other diseases that may interfere with drug absorption, distribution, metabolism or excretion;
10. Monoamine oxidase inhibitors (MAOIs) are taken by subjects now or within 2 weeks before screening. Subjects who took antipsychotics, antidepressants or mood stabilizers before randomization and these drugs' cleaning phase had less than five half-lives. Subjects who took fluoxetine within 1 month before screening. Subjects who continue to take Chinese medicines with antidepressant effects specified in the instructions after signing informed consent.

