## **Observation measures**

### **Validity Index**

#### **Main efficacy measures**

Changes of MADRS score at therapeutic visit point compare with baseline.

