2.1 Study Overview

This is a randomized, parallel-group, placebo-controlled and double-blind study conducted by a single center. In the study, ethosuximide or placebo will be given for 2 weeks in experimental group or control group and escitalopram will be given for the next 4 weeks in each group.

usage and dosage:

Ethosuximide, 2 times/day, take it orally after breakfast/dinner; take 500mg in the morning and 500mg in the evening on day1, 500mg in the morning and 750mg in the evening on day2, 750mg in the morning and 750mg in the evening on day3, 750mg in the morning and 1000mg in the evening on day4, 1000mg in the morning and 1000mg in the evening on day5, maintain this dose until the end of treatment for 2 weeks.

The usage and dosage of placebo are the same as above.

Escitalopram, 1 time/day, 20mg/day, take it orally after breakfast, take it for 4 weeks without interruption.

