5.3.2 Demographic and Baseline Characteristic

Baseline characteristics

	Ethosuximide + Escitalopram(n)	Placebo + Escitalopram(n)
Age, years		
Sex, F (% n/N)		
BMI, kg/m ²		
Years of education		
Vital signs		
Blood pressure (sitting position)		
Heart rate		
Respiratory rate		
Body temperature		
Physical examination of clinical significance		

Abnormal values of laboratory examination

Abnormal results of 12-Lead Electrocardiograms

Age at onset of first major depressive episode (years)

Lifetime number of major depressive episodes

Duration of current episode (weeks)

Montgomery–Åsberg Depression Rating Scale (MADRS) score

Young Mania Rating Scale (YMRS) score

Hamilton Anxiety Rating Scale (HAMA) score

Quick Inventory of Depressive Symptomatology – Self Report (QIDS-SR) score

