5.4 Clinical Efficacy of Drug Treatment Analysis

The efficacy of drugs will be judged by analyzing the changes from baseline to treatment point in each scale score. Two-way Repeated Measures Anova will be used to compare the efficacy between experimental and control group; intervention measures will be defined as inter-group variables, and time points of scale evaluation as inner-group variables. First, the scale scores of each participant at baseline and each treatment point be listed (Table 2), and the average value of each group will be calculated. Then, values of sum of squares of deviation from mean, degree of freedom and mean square will be calculated. After calculating F values of inter-group factors or inner-group variables, the corresponding P values by querying F value threshold table and statistical inferences will be determined. It should be noted that the degree of freedom of inner-group variables needs to be corrected in the statistical test.

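### The efficacy ANOVA has only group and time as terms: the baseline score is not a covariate, and the SAP does not say whether baseline is a level of time

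*SAP*

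**What the plan says.** The protocol's primary measure is "Changes of MADRS score at therapeutic visit point compare with baseline", and SAP 3.1.1 repeats it. SAP 5.4 agrees at first: "The efficacy of drugs will be judged by analyzing the changes from baseline to treatment point in each scale score". It then specifies a two-way repeated measures ANOVA in which "intervention measures will be defined as inter-group variables, and time points of scale evaluation as inner-group variables", with F values for those two kinds of factor. Its first calculation step is that "the scale scores of each participant at baseline and each treatment point be listed (Table 2"), followed by group averages.

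No covariate is named in SAP 5.4 or elsewhere in the SAP, and the protocol contains no analysis model. Baseline MADRS, QIDS-SR, HAMA and YMRS are collected at Visit 1 and appear in the baseline table of SAP 5.3.2. The levels of the time factor are not listed.

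**The concern.** There are two gaps. First, on any reading the model contains only group and time. If change scores are analysed, baseline is subtracted with a fixed coefficient of 1 instead of one estimated from the data. This wastes precision unless the slope of follow-up on baseline is close to 1. It also leaves part of any chance baseline difference in the treatment estimate. That matters more with 20 per arm and no stratification stated under Random method in the protocol.

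Second, the text points two ways on the time factor. Judging efficacy by change suggests nine post-baseline levels (Visits 2 to 10). Starting from scores at baseline and each treatment point could mean ten levels of raw score. These are different analyses with different power, and the choice should not remain open until the data are seen.

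**Working it through.** **Inputs from the documents.** 20 per arm (SAP 2.2); nine post-baseline visits with scale scores (Visits 2 to 10), six of them in the two study-drug weeks (Visits 2 to 7). No SD, correlation, effect size, alpha or power is given, so the sample size cannot be reproduced.

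**Assumptions.** Two-sided alpha 0.05; follow-up SD s1 = 9; effect 4.5 points (0.5 SD). The baseline SD is s0, the baseline-to-follow-up correlation rb, and the correlation between follow-up visits rp. Two ranges are used:
- (A) s0 of 4.5 to 6 and rb of 0.3 to 0.5. This suits MADRS, because selection acts directly on that score: "The subjects who will score more than or equal to 22 points on the MADRS scale at screening and baseline period", and exclusion of a "Subject whose score of MADRS scale in baseline period will be 25% lower than that in screening period".
- (B) s0 = 9 and rb of 0.3 to 0.7. QIDS-SR and HAMA have no entry threshold, so equal SDs are less implausible there.

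**Formulas**, for the mean of k visits per patient:
- Vpost = s1²(1 + (k−1)rp)/k
- Change score: V = Vpost + s0² − 2·rb·s0·s1, 38 df
- Baseline-adjusted: V = (Vpost − rb²·s1²)(1 + 1/36), 37 df
- Power from the noncentral t with standard error √(2V/20)

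Before the 1 + 1/36 penalty, adjustment removes (s0 − rb·s1)² from the variance. This is zero when rb·s1/s0 = 1, for example at s0 = 4.5 and rb = 0.5.

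**Worked case** (s0 = 6, rb = rp = 0.3, k = 9). Vpost = 81 × 3.4/9 = 30.6. Change: 30.6 + 36 − 32.4 = 34.2, power 66.0%. Adjusted: (30.6 − 7.29) × 37/36 = 23.96, power 80.8%.

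**Range A, constant effect, mean of Visits 2 to 10** (power, change / adjusted):

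| s0 | rb | rp = rb | rp = 0.7 |
|---|---|---|---|
| 4.5 | 0.3 | 76.8 / 80.8 | 46.2 / 47.4 |
| 4.5 | 0.5 | 79.6 / 78.5 | 60.1 / 58.9 |
| 6 | 0.3 | 66.0 / 80.8 | 41.6 / 47.4 |
| 6 | 0.5 | 76.1 / 78.5 | 57.8 / 58.9 |

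**Range A, other layouts** (change in power from adjustment, in points):
- Effect only at Visits 2 to 7 but nine visits averaged (effect 4.5 × 6/9 = 3.0): −1 to +12 if rp = rb; −1 to +3 if rp = 0.7.
- The same effect averaged over Visits 2 to 7: −1 to +14 if rp = rb; −1 to +6 if rp = 0.7.
- Day 14 alone: −1 to +3. Net variance gain is −2.8% to +10.5%.
- Correlation falling with days between visits, mean of Visits 2 to 10: −1 to +6.

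**Range B, constant effect, mean of Visits 2 to 10.** +11 to +39 points if rp = rb; +11 to +17 if rp = 0.7; +19 to +32 with decaying correlation. Day 14 net variance gain is +13% to +33%.

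**Worst case for adjusting.** With slope exactly 1, the only effects are the 1/36 = 2.8% inflation and one lost df. The largest loss is 1.25 points, where change-score power is 67%.

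**Chance imbalance in range A.** The SD of the baseline mean difference is s0·√(2/20), which is 1.42 for s0 = 4.5 and 1.90 for s0 = 6. A difference of 2 points or more therefore occurs in 16% and 29% of trials. A 2-point difference shifts the change-score estimate by 2(rb·s1/s0 − 1), in table order −0.8, 0, −1.1 and −0.5 points. The adjusted estimate shifts by 0. In those trials alone a true null is rejected 5–10% of the time with change scores and 4–6% with adjustment. Over all trials, type I error was 4.6–5.3% (20,000 simulated trials per setting).

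**Levels of time.** Nine levels give uncorrected within-subject df of 8 and 8 × 38 = 304; ten give 9 and 9 × 38 = 342. With ten levels the group main effect includes a visit whose expected difference is zero, so a constant effect is multiplied by 0.9. With equal SDs and a common correlation of 0.3 / 0.5 / 0.7, group-main-effect power is 42% / 54% / 76% for nine-level change scores and 63% / 46% / 37% for ten-level raw scores. The 0.9 factor does not apply to the group-by-time interaction, for which no power was computed.

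**The case against.** Analysing change in a randomised 1:1 trial is valid, and change scores are the more natural reading of SAP 5.4, since listing scores may only be the step that produces the changes. For MADRS the gain may be nil. At s0 = 4.5 and rb = 0.5 adjustment loses about one point in every layout.

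The larger figures need favourable settings. +15 requires scores a day apart to correlate no better than baseline with Day 42. It also requires a constant effect to Day 42, although study drug lasts two weeks and "escitalopram will be given for the next 4 weeks in each group". +39 requires equal SDs, offered only for secondary scales, whose scores may also be narrowed indirectly by selection on MADRS and the exclusion of anxiety disorders. The imbalance figures are the same efficiency loss seen conditionally, not a second problem. YMRS, which may sit near its floor, and the individual MADRS items were not computed. If the slope may differ by visit, the within-subject error df fall by 8 (from 304 to 8 × 37 = 296), not by one.

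All of this stands, and it limits the weight of the point. It does not reverse the balance: the loss is bounded at about 1.3 points, the possible gain is much larger, and the data are already collected. Nor does it supply the missing list of time levels.

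**Conclusion.** The concern holds. The efficacy model omits the baseline score as a covariate and does not say whether baseline is a level of time. This is a matter of precision and specification, not of validity. The plan should be changed, but the trial's conclusions do not depend on it.

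For MADRS the likely benefit is modest: −1 to +6 points if follow-up visits correlate at 0.7 or with decaying correlation, and up to +15 only if they correlate no better than with baseline. For QIDS-SR and HAMA it could be larger, +11 to +39 points if baseline and follow-up SDs are equal. Every figure rests on the assumed SDs, correlations and effect, so confidence in the size is moderate. The absence of the covariate is plain from the text. Taken alone, the unstated time levels would be a missing detail; the same edit settles both.

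**What to change.** In SAP 5.4:
- State that the dependent variable is change from baseline at post-baseline visits.
- List the levels of the time factor and limit them to post-baseline visits.
- Add the baseline value of the same scale as a continuous, mean-centred covariate, for MADRS and each secondary scale score.
- Report the adjusted mean difference with its 95% CI.

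The cost is one or two sentences, one degree of freedom in the between-group test, about 2.8% variance inflation and no new data. Which visit or window is primary is a separate decision that this change does not settle, and it may affect power more than the covariate does.

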5.5 Safety Analysis

5.5.1 Adverse events

Adverse events occurred in experimental and control group will be summarized according to following contents.

1. Any treatment emergent adverse events
2. Related treatment emergent adverse events

3. Serious treatment emergent adverse events
4. Adverse Events Leading to Treatment Discontinuation
5. Adverse Events Leading to Death
6. Any treatment emergent adverse events by severity
7. Related treatment emergent adverse events by severity

These events will be displayed in data lists.

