### **Methods of drug administration**

Subjects with treatment-resistant depression who meet the inclusion criteria and do not meet the exclusion criteria are randomly assigned to the following two study groups:

Group 1: A (2 weeks) + C (4 weeks)

Group 2: B (2 weeks) + C (4 weeks)

A: Ethosuximide (capsule, 250mg/capsule)

B: Placebo (capsule, 250mg/capsule)

C: Escitalopram (tablet, 10mg/pill)

usage and dosage:

Drug A, 2 times/day, take it orally after breakfast/dinner; take 500mg in the morning and 500mg in the evening on day1, 500mg in the morning and 750mg in the evening on day2, 750mg in the morning and 750mg in the evening on day3, 750mg in the morning and 1000mg in the evening on day4, 1000mg in the morning and 1000mg in the evening on day5, maintain this dose until the end of treatment for 2 weeks.

The usage and dosage of Drug B are the same as above.

Drug C, 1 time/day, 20mg/day, take it orally after breakfast, take it for 4 weeks without interruption.

The time of the first administration should be after the next day's breakfast randomly. If the patient had taken escitalopram or was allergic to escitalopram in the past, the researchers would choose another appropriate antidepressant according to the patient's condition. Medication cycle: The study drugs will be taken for 6 weeks.

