**A Randomized, Parallel-group, Placebo-controlled, Double-blind Clinical Trial to
Evaluate the Efficacy and Safety of Ethosuximide in Chinese Patients with
Treatment-Resistant Depression**

Statistical Analysis Plan

(Registration Number: 2019-716)

Version Number: 2.0 Date:12 April 2019 (Protocol version Number: 3.0)

1. Study purpose

The aim of this study is to evaluate the clinical efficacy and safety of ethosuximide in patients with treatment-resistant depression.

2. Study design

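### SAP 5.5.1 summarises adverse events by arm with no onset window and no split by treatment phase, although the arms differ in randomised drug only for the first 2 of 6 weeks

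*SAP*

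**What the plan says.** SAP section 1 sets the target: "The aim of this study is to evaluate the clinical efficacy and safety of ethosuximide in patients with treatment-resistant depression".

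SAP 2.1 sets the sequence: "ethosuximide or placebo will be given for 2 weeks in experimental group or control group and escitalopram will be given for the next 4 weeks". The Protocol (Methods of drug administration) gives the same sequence. It adds that a patient who has already taken escitalopram, or is allergic to it, may be given a different antidepressant. Within the first phase the assigned dose rises daily to Day 5, after which the instruction is to "maintain this dose until the end of treatment for 2 weeks".

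On adverse events, SAP 5.5.1 reads: "Adverse events occurred in experimental and control group will be summarized according to following contents". The seven categories are any, related, serious, leading to discontinuation, leading to death, any by severity and related by severity. It ends: "These events will be displayed in data lists". It does not define *treatment emergent*, give an onset window, split by phase, name a denominator, or say which drug *related* and *discontinuation* refer to. SAP 4.2 defines a single Safety Set. The baseline table shell in SAP 5.3.2 heads each arm with its two-drug sequence.

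The Protocol's visit lists record adverse events at baseline, on Days 2, 3, 4, 6, 10 and 14, and again around Days 22, 29 and 42.

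**The concern.** The randomised contrast between ethosuximide and placebo lasts two weeks. After that both arms are meant to receive the same drug. An arm-level adverse event table with no window is most naturally filled with everything recorded up to Day 42. Such a table answers a question about two treatment sequences, whereas the stated aim is the safety of ethosuximide.

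Three things are at stake. Second-phase events common to both arms would pull per-patient percentages together and make ethosuximide look closer to placebo than it was while it was being taken. An event counted as *related* or as leading to discontinuation could refer to either of two drugs. And because the window is open, it could be chosen after the events are known.

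**Working it through.** The plan gives no adverse event rate, safety precision target or test for adverse events, so there is no figure of its own to reproduce. The check has three parts.

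**1. Exposure time.** Inputs: 2 weeks and 4 weeks (SAP 2.1; Protocol, Methods of drug administration).
- 14 + 28 = 42 days.
- 14/42 = 33% of planned treatment days carry the randomised contrast; 28/42 = 67% follow it.
- These are shares of days, not of events.

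**2. Effect of counting over the whole sequence.** Two assumptions are needed, because the SAP states neither: each patient counts once, and onset may fall anywhere in the 42 days. Let pE and pP be the first-phase risks on ethosuximide and placebo. Let p2 be the second-phase risk, equal in both arms and independent of the first phase.
- Whole-period risk = 1 − (1 − p1)(1 − p2), where p1 is pE or pP.
- Whole-period difference = (pE − pP)(1 − p2).

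With assumed first-phase risks of 60% and 30%:

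| Assumed p2 | Experimental | Control | Difference (points) | Ratio |
|---|---|---|---|---|
| 0% | 60% | 30% | 30 | 2.00 |
| 10% | 64% | 37% | 27 | 1.73 |
| 30% | 72% | 51% | 21 | 1.41 |
| 50% | 80% | 65% | 15 | 1.23 |
| 70% | 88% | 79% | 9 | 1.11 |

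The difference depends only on pE − pP and p2. First-phase risks of 50% and 20% also give 21 points at p2 = 30% (65% against 44%) and 15 points at p2 = 50% (75% against 60%). With 20 patients per arm (SAP 2.2), 30 points is 0.30 × 20 = 6 patients and 21 points is 0.21 × 20 = 4.2 patients.

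If the second-phase risks differ (qE and qP), the whole-period difference is (1 − pP)(1 − qP) − (1 − pE)(1 − qE). Take 60% and 30% with qP = 30%, so that the first term is 0.7 × 0.7 = 0.49:
- qE = 20%: 0.49 − 0.4 × 0.8 = 0.17.
- qE = 40%: 0.49 − 0.4 × 0.6 = 0.25.
- qE = 52.5%: 0.49 − 0.4 × 0.475 = 0.30, the point at which the shrinkage is fully offset.

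For a rare category the difference hardly moves: an assumed p2 of 2% gives a factor of 0.98. There the issue is which drug the event belongs to.

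**3. Is the split supplied elsewhere in the SAP?** Vital signs (5.5.2) and SAFTEE events (5.5.6) are tabulated by time point. Laboratory and ECG changes (5.5.4, 5.5.5) are also listed by time point. None of these gives the related, serious, discontinuation or severity categories by phase. The Protocol's visit lists do not name SAFTEE, although it is among the safety indices; the flow chart was not available in the text reviewed.

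**The case against.** The strongest reply is that the SAP contains no pooling rule. Section 5.5.1 is silent on the window and on whether patients or events are counted, so the formula above rests on a reading. That stands: a reader might infer that the plan prescribes a six-week count, and the documents do not say so. The silence still has to be resolved, and the headings and recording period point towards the whole sequence.

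A reader might also infer that events cannot be tied to a drug or dose at all. The documents do not support that. Adverse events are recorded at six visits from Day 2 to Day 14, the assigned dose is fixed by day, and listings are planned. The limit lies in the planned summaries, not in the data.

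Nor is it right that treatment-emergent events are never shown over time: SAP 5.5.6 plans this for SAFTEE. That reduces the gap without closing it.

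Two further points are fair. The whole-period comparison remains a valid randomised comparison of two sequences. And equal second-phase risk is not assured, because some patients may receive a different antidepressant and those with intolerable events leave the study. The first supports keeping the six-week table; the second is why the size is only approximate. Finally, 5.5.1 plans no hypothesis test, so no planned test loses power; the issue is what the reported percentages describe.

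**Conclusion.** The point holds as a gap in specification with a predictable consequence. SAP 5.5.1 gives neither a treatment-emergent window nor a phase split, and on its default reading the arm-level table is not specific to ethosuximide.

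The day counts are firm. The attenuation is conditional: about (1 − p2) for a per-patient any-event difference, provided that second-phase risk is similar in the two arms and independent of the first phase. A 30-point difference becomes 27, 21, 15 or 9 points as p2 runs through 10%, 30%, 50% and 70%. All these rates are assumed. The difference could be preserved or widened if the experimental arm had a much higher second-phase risk.

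The data already planned should allow the split, so this is a matter of stating the analysis rather than a defect in the design.

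**What to change.** In SAP 5.5.1:

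- Define *treatment emergent*, and produce each of the seven summaries twice: for onset before the first second-phase dose (denominator: Safety Set), and for onset from that dose on (denominator: patients entering that phase). Name the first as the ethosuximide safety comparison.
- Record for each event the drug to which *related* and *leading to discontinuation* refer, by investigator judgement. A calendar rule that charges every event to the drug being taken at onset would misassign carry-over from ethosuximide.
- Flag events that continue across the switch or start soon after it. The sponsor should set that interval in advance.
- Show the assigned dose on the onset day as a descriptive listing only. In the fixed escalation everyone follows the same order of doses, so dose and time are confounded.
- State whether patients or events are counted, and keep the six-week total as a supplementary table.

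The cost is SAP wording and one more set of tables, with smaller counts in each. No new visit or patient is needed. The visit lists mention adverse event records without saying what they contain, so the sponsor should confirm that onset date and the drug judged responsible are captured.
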